# **HIT Group patients:**

i) Intelligence Quotient: see definition in HIT 2000 study protocol – Appendix 5.

ii) Degree of leucoencephalopathy: see definition in HIT 2000 study protocol – Appendix 5.

## 13.5 Interim and final analyses

Interim analyses will be performed two and four years after the start of the study. The final evaluation with study report will be performed after seven years. If an interim analysis shows significantly superior EFS in one of the treatment arms the study will be closed. If other studies show that the main question of the study is answered, the study steering committee together with the DMSC will decide on closure of the study.

The design of this trial may be changed, if necessary, in case of new important discoveries. Modifications of the protocol will be made only in the form of written amendments and with the agreement of the study committee. The respective ethic commissions have to be informed of the modifications.

If an adjustment of the group sequential design is necessary e.g. because of a low recruitment rate - the respective changes of the time points, number of interim analyses, maximal sample size and a-spending function will be done according to the conditional rejection error probability method by Schäfer and Müller (reference below). The modifications can be done during a planned or unplanned interim analysis on the basis of the observed data collected so far. The corresponding conditional rejection error probability functions are defined by Schäfer (reference below). If a design change is made, the time point, the data file of the trial, all calculations and the description of the new group sequential

design have to be recorded in the amendment.

Reference: Schäfer H, Müller H-H: Modification of the sample size and the schedule of interim

analyses in survival trials based on data inspections. Statistics in Medicine 2001; 20:

3741-51.

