#### 1. FLOW DIAGRAMS

## 1.1 Summary of the Study

[figure not shown]
This protocol has been reviewed by the SIOP Scientific Committee in September 2002 and approved as a SIOP clinical trial in regard to the importance of the questions being addressed and the quality of the science. However, SIOP is not a clinical trials organisation and therefore cannot be held responsible for the overall conduct of the study which rests with the treating physicians and each individual country's childhood cancer trials organisation.

With this protocol the GPOH and the SIOP PNET 4 Study Committee presents a a randomised trial for the treatment of standard risk medulloblastoma in children and adolescents. Possible changes or amendments to the protocol will be communicated by the appropriate National Co-ordinator to participating institutions. Participating centers are requested to ensure the validity of their available protocols.

Centres wishing to participate in the PNET 4 study should be able to comply with every aspect of the study protocol including all the quality control procedures.

The Study Commitee emphasizes that even following approval from the ethics committees of paticipating centres, no legal responsibility for possible consequences resulting from the application of recommendations from this protocol will be taken by the members of the study committe. Treatment and follow-up of patients with medulloblastoma requires a high degree of medical care existing only in hospitals with adequate infrastructure. Significant complications from the underlying disease or from its treatment can develop in every patient at any time and may require a full range of resources including intensive care. Children with medulloblastoma should thus be treated by an experienced team and interdisciplinary cooperation is a prerequisite for such a team including experienced neurosurgeons, neuropathologists, neuroradiologists, radiotherapists, pediatricians and nurses.

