### 13. STATISTICAL CONSIDERATIONS

# 13.1 Study design

The study is a comparison between treatment with hyperfractionated radiotherapy and conventional RT with a reduced craniospinal dose in patients with Medulloblastoma without metastases in the age group 4-21 years. The lowest age limit may differ between national groups but must not be lower than 4 years at the day of surgery. Recruitment of patients will last until 31.12.2005. Thereafter a prolongation of the study is possible, (see 13.5), and will be the case in order to recruit the necessary number of patients to reach the desired statistical power. The information of the about the recruitment rate in the HIT study in the first two years of the trial should not be used. A 2-year observation time will be undertaken following closure of the study.

After parental/patient consent every patient in the study will be randomised to one of the two treatment arms. The randomisation will be by block randomisation undertaken at the relevant National Data Centre. Randomisation will be stratified according to sex and the presence of residual tumour (see 5.1.c) on postoperative scan.

GCP of ICH and the Declaration of Helsinki will be respected in the study.

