# 14. Data Monitoring and Safety Committee (DMSC)

An independent DMSC composed of 3 international experts will monitor the progress of the trial on ethical and scientific backgrounds. The role of the DMSC will be:

- to review accrual rate
- to examine interim analyses

Each interim analysis will be reported to the DMSC.

- these interim analyses will remain confidential
- on the basis of these analyses, the DMSC will recommend whether the study can continue, or whether it should be changed or terminated prematurely.

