#### 2. The Protocol

All national groups will use a common protocol for the international study except for HIT Group centres that will use the original HIT 2000 protocol with appropriate amendments in relation to the common study, HIT-SIOP PNET 4. The finalised master protocol in the English language will be held at the International Data Centre. Other national groups will be responsible for producing a literal translation in their own language.

Each national co-ordinator will be responsible for the distribution of protocols to centres within their national group via their national data centre as appropriate.

Appendices may be added independently by any of the national groups to address local needs, provided they have no bearing on the essential aims of the international protocol. However no change will be allowed to the eligibility criteria or the treatment procedures of the main protocol.

Subsequent to finalisation, the study chairman and the national co-ordinators must agree any amendments to the protocol.

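### If the group sequential design is changed on observed data, section 13.5 puts the data file and all calculations in the amendment, which conflicts with the confidentiality of interim analyses in section 14

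*Protocol*

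**What the plan says.** Section 13.5 permits changes to the analysis times, the number of interim analyses, the maximal sample size and the alpha-spending function, with a low recruitment rate as its example of a reason. Such a change "will be done according to the conditional rejection error probability method by Schäfer and Müller". On the data used it says: "The modifications can be done during a planned or unplanned interim analysis on the basis of the observed data collected so far". On documentation it says: "If a design change is made, the time point, the data file of the trial, all calculations and the description of the new group sequential", and the sentence ends "design have to be recorded in the amendment".

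The handling of amendments is described in three places:
- Section 13.5 requires written amendments agreed by the study committee, and the ethics commissions must be told of the modifications.
- Appendix B, item 2, says that "the study chairman and the national co-ordinators must agree any amendments to the protocol".
- Section 1.1 says that "amendments to the protocol will be communicated by the appropriate National Co-ordinator to participating institutions".

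Section 14 has each interim analysis reported to the DMSC and adds "these interim analyses will remain confidential". The same section asks the DMSC to review any major modification before it is implemented. Appendix B, item 7, releases interim data to the trial statistician.

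**The concern.** The conditional rejection error method is a sound way to change a design on observed data and keep the type I error. The concern is only where its working is written down. The working depends on the between-arm log-rank statistic, so a full record of it is a record of the interim treatment comparison. Section 13.5 assigns that record to a document that the trial's leadership must agree and that is communicated to institutions.

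Treatment is open (once-daily against twice-daily radiotherapy). If those who enter and follow patients knew the interim difference while the trial was running, entry could become selective, patients could be switched between arms, and imaging beyond the six-monthly minimum in section 11.1 could differ by arm. Control of alpha does not protect the EFS comparison against any of these. The sponsors recognise the hazard: the introductory list of agreed changes bars national analyses that might harm accrual.

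**Working it through.** **1. The rules side by side**

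| Question | Source | Answer |
|---|---|---|
| What is recorded after a design change? | 13.5 | Time point, data file, all calculations, new design |
| Where? | 13.5 | In the amendment |
| On what data may the change rest? | 13.5 | Observed data at a planned or unplanned interim |
| Who must agree an amendment? | 13.5; Appendix B, item 2 | Study committee; study chairman and national co-ordinators |
| To whom are amendments communicated? | 1.1 | Participating institutions |
| Status of interim analyses? | 14 | Reported to the DMSC; confidential |
| Restricted annex or redacted version? | none found | Not provided for |

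Taken literally, the second and sixth rows cannot both be met once a change has been made on observed data.

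**2. The design being modified.** Section 13.8 gives levels of 0.005, 0.005 and 0.04, and 0.005 + 0.005 + 0.04 = 0.05, the stated overall level. Section 13.10 gives accrual of 33.6 per year for 2.8 years, then 102.7 per year to year 5: 33.6 × 2.8 + 102.7 × 2.2 = 320.0, the stated target. Both figures reproduce.

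**3. How much the calculations reveal.** This takes the year-4 look of section 13.5 and the final analysis at year 7.
- Hazard at 70% 3-year EFS: −ln(0.70)/3 = 0.1189 per year. At 85%: −ln(0.85)/3 = 0.0542 per year.
- Expected events by time t from accrual at rate r between a and b: r × [(b − a) − (e^(−h(t−b)) − e^(−h(t−a)))/h], with b cut at t.
- With 70% in both arms: 33.1 events at year 4 and 114.7 at year 7, so the information fraction is τ = 33.1/114.7 = 0.288.
- With 70% against 85%: 24.6 and 87.0 events, τ = 0.283.
- Final critical value for two-sided 0.04: c = 2.054.
- Conditional probability of crossing the final bound, given interim z: Φ(−(c − z√τ)/√(1−τ)) + Φ((−c − z√τ)/√(1−τ)).

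Worked at z = 2 and τ = 0.288 (√τ = 0.537, √(1−τ) = 0.844): (2.054 − 1.074)/0.844 = 1.161, upper tail 0.1227. The opposite tail is 0.0001. Sum 0.123.

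| Interim \|z\| | Two-sided, τ = 0.288 | Favoured-side tail only, τ = 0.283 |
|---|---|---|
| 0 | 0.015 | 0.0076 |
| 1 | 0.037 | 0.0362 |
| 1.5 | 0.070 | 0.0690 |
| 2 | 0.123 | 0.1213 |
| 2.5 | 0.200 | 0.1964 |

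The values rise strictly with |z|, and the choice of event-rate assumption barely moves them. A printed two-sided value therefore gives back |z| but not its sign. A one-sided value for a named arm gives back z itself: z = (c − √(1−τ) × Φ⁻¹(1 − p))/√τ. With the 24.6 events expected at year 4, z = 1 corresponds to a hazard ratio of about exp(−2/√24.6) = 0.67, and z = 2 to about exp(−4/√24.6) = 0.45. The sign is in any case contained in the data file and in a complete set of calculations, both of which 13.5 requires.

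**The case against.** The strongest reply is that 13.5 sets only an audit duty. A patient-level file is hardly going to be printed in an amendment. Read with section 14 and Appendix B, item 7, the sensible practice is for the statistician and the DMSC to hold the record while the design change alone is circulated. That is good practice and is what the fix asks for, but the sentence names the amendment as the place of record, for the calculations as well as the data file.

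Other parts of the reply stand:
- **Delivery to clinicians is inferred.** No sentence says that randomising clinicians will see EFS by arm. The conclusion comes from joining 13.5, Appendix B and section 1.1.
- **The rule is conditional.** A reader might infer from section 13.1 ("Thereafter a prolongation of the study is possible, (see 13.5), and will be the case") that the route was bound to be used. The text does not support this: recruiting for longer to reach the planned 320 need not alter the sequential design. Neither listed amendment makes such a change.
- **The probability alone is not the whole result.** A reader might infer that one printed value discloses the signed statistic. A two-sided value does not.
- **Timing.** The current version is dated July 2010. Section 13.5 sets the final evaluation at seven years from a start in January 2001, and section 4.7.3.1 already cites a 2010 report on EFS. The harm through accrual depends on accrual still running, so the practical gain from amending this version is limited.

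A further temptation is to require that changes for low recruitment use only pooled data and keep the significance levels. That would restrict a valid method that 13.5 deliberately allows, including changes to the looks and the spending function. It is a separate design choice and forms no part of this point.

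**Conclusion.** The point holds as a conflict between two operative rules. If the group sequential design is changed on observed data, following 13.5 to the letter places comparative interim EFS information in a document that must be widely agreed and is communicated to institutions, contrary to section 14. Type I error control is unaffected.

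The size is qualitative: the calculations reveal |z|, and the data file and full working also reveal the direction. No bias, loss of power or inflation of alpha has been quantified. The illustrative probabilities rest on the accrual in 13.10, constant hazards, no loss to follow-up and looks at years 4 and 7. The conclusion about wording rests on none of these. A reader might infer that interim results were in fact disclosed; nothing in the protocol shows that. The matter should be corrected, but it is a drafting defect with a conditional consequence.

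**What to change.** Change the last sentence of the design-modification paragraph in 13.5 so that it says, in substance: the data snapshot, the interim statistic and all conditional-error calculations are recorded in a dated confidential report held by the trial statistician and the DMSC until the final analysis; the circulated amendment states only the time point of the change and the new design parameters, namely sample size, analysis times and significance levels. A cross-reference to section 14 would make the two sections agree.

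The full audit trail is kept, and only its holder and release date change. The cost is one wording amendment. The small downside is that the study committee, national co-ordinators and ethics committees would accept a redesign on the DMSC's recommendation without seeing the comparative data.

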### 13.6 Serious Adverse Events

Serious Adverse Events (section 12) should be reported to the National Data Centre within 24 hours of the knowledge of the event, which will transmit the information to the International Data Centre. Transmission of this information will be done to the DMSC when appropriate. Toxicity analysis will be performed every 6 months and will be forwarded to the DMSC who will decide whether and how the study will proceed.

# 13.7 Stopping Rules for Audiological toxicity

A Kaplan-Meier estimation of ototoxicity (p) will be calculated separately for each arm. Any grade 3 or grade 4 toxicity as defined by the HIT Group criteria (section 10.4.4) will be considered as an event. The stopping rule will focus on the Kaplan-Meier estimation for ototoxicity noted on the post treatment audiograms. At these time points the number of toxic events should not exceed 20%.

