## 4.7.6 Audiology

High frequency hearing loss progressing to involve the speech frequency range (500-3,000 Hz) is a HIT-SIOP PNET 4 Protocol Version 3.0, 27th July 2010 (RG 10-034)

major toxicity of cisplatin. It is clear that the ototoxicity is dependent upon the cumulative dose of cisplatin, but other factors such as the dose per course and drug scheduling may be important. This effect is compounded by the effect of young age, the tumour itself, preceding cranial irradiation and dark eye colour 99. Of the 65 patients treated in CCG 9892, 21 (32.3 %) developed Grade 3 or 4 ototoxicity. In these patients, hearing loss occurred as early as the third cycle of CCNU, cisplatin, vincristine chemotherapy and as late as the seventh cycle. Ototoxicity was the principal reason for dose modification or curtailment of chemotherapy. By contrast, Grade 3 or 4 ototoxicity occurred in only 11 % of patients with medulloblastoma treated on the maintenance arm of the HIT 91 study, despite similar chemotherapy. The difference between the incidence of ototoxity noted in CCG 9892 and HIT 91 probably mainly reflects the difference in Cisplatin dose modification criteria used in these two studies.

Monitoring of hearing loss is a fundamental and mandatory part of this study. In PNET 4, the ototoxicity grading system devised for both HIT 91 and HIT 2000 will be used. Similarly, dose modification in PNET 4 will be that used in these two HIT Group studies. It is thus anticipated that ototoxicity associated with PNET 4 be significantly less than that reported from studies using Cisplatin containing maintenance therapy performed by the COG Group and elsewhere.

It is, however, appreciated that it is important to compare accurately the ototoxity following treatment according to the PNET 4 trial with other studies in which the Brock/CTC grading system  $^{100}$  ototoxity is generally used. In this respect, it is mandatory for patients entered into PNET 4 to have a pure tone audiogram performed at the end of treatment. Hearing loss at this time will be graded according to the Brock/CTC system and recorded either on the study Data Forms or, in the case of HIT Group patients, a hard copy of the audiogram will be sent the HIT Group National Data Centre.

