**Data to be collected:** Pure tone audiometry (PTA) will be undertaken before therapy and before every subsequent course of chemotherapy and graded according to the HIT scoring system (section 10.4.4). Chemotherapy will be modified on the basis of ototoxicity (section 10.4.4). Audiology will also be monitored as a late effect of treatment (section 10.4.4 and table in section 1.5) with the audiogram at end of treatment being graded according to the Brock/CTC system as described above.

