# 10.2 Investigations during chemotherapy

# 10.2.1 Investigations before each course of chemotherapy.

- a) Clinical exam with neurological exam.
- b) Full blood count.
- c) Blood biochemistry electrolytes (ionogram), urea, creatinine, ALT, AST, Alkaline phosphatase, bilirubin, albumin, magnesium, calcium, phosphate).
- d) Audiology (mandatory) Pure Tone Audiometry if possible.
- e) Glomerular filtration rate if estimated from plasma creatinine level (see appendix K).

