# 10.4.4 Ototoxicity:

The Ototoxicity Grading System in PNET 4 is that used in the HIT 91 and HIT 2000 studies, as follows:

Grade 0: normal

Grade 1: ≤ 15 dB at ≤ 2000 Hz

Grade 2: 16-30 dB at ≤ 2000 Hz

Grade 3: 31-60 dB at ≤ 2000 Hz

Grade 4: >60 dB at ≤ 2000 Hz

It is, however, mandatory, for patients to have a Pure Tone Audiogram performed at the end of treatment. This audiogram will be either sent to the National Data centre or the grading recorded on the data forms and be graded according to both the HIT and Brock/CTC grading systems (Appendix L) to enable a comparion of ototoxicity between different treatment studies.

The Dose Modification of cisplatin is based on the sytem used in the HIT 91 and HIT 2000 studies, as follows:

Hearing – PTA	Dose Modification
< 16 dB at 1000-3000 Hz or ≤ 40 dB at 4000-8000 Hz	None
16-30 dB at 1000-3000 Hz or > 40 dB at 4000-8000 Hz	Substitute Carboplatin 400 mg/m  for Cisplatin
> 30 dB at 1000-3000 Hz	Omit any platinum

Grading for Audiometry is based on loss in both ears — Thus the grading (including that for modification of chemotherapy) is based on the Highest Grading i.e. the 'worst ear'.

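### Section 13.7 ties the only numeric ototoxicity limit to post-treatment audiograms, about 15 months after surgery, and does not clearly count grade 3–4 loss found by the audiology required before every course

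*Protocol*

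**What the plan says.** Section 13.7 plans a separate Kaplan-Meier estimate of ototoxicity in each arm. On the event it says: "Any grade 3 or grade 4 toxicity as defined by the HIT Group criteria (section 10.4.4) will be considered as an event". On the data: "The stopping rule will focus on the Kaplan-Meier estimation for ototoxicity noted on the post treatment audiograms". On the limit: "At these time points the number of toxic events should not exceed 20"%. No other section gives a trial-level ototoxicity limit.

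Earlier data on the same scale are part of the plan. Section 4.7.6 states: "Pure tone audiometry (PTA) will be undertaken before therapy and before every subsequent course of chemotherapy and graded according to the HIT scoring system". Section 10.2.1 lists, before each course: "Audiology (mandatory) Pure Tone Audiometry if possible". Section 10.4.4 adds the final test: "It is, however, mandatory, for patients to have a Pure Tone Audiogram performed at the end of treatment". The schema in section 1.5 places audiology at the end of chemotherapy, at 3 and 5 years and at age 20, so the end-of-chemotherapy audiogram is the earliest one that can count as post-treatment.

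Section 12 takes grade 3–4 ototoxicity out of SAE reporting. It says that ototoxicity will be monitored and points to section 13.7 for the stopping rule. Sections 13.6 and 14 send a toxicity report to the DMSC every six months.

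**The concern.** The limit is a safety boundary for a toxicity that accumulates over the course of treatment. Of the earlier study of reduced-dose craniospinal radiotherapy followed by the same three drugs, section 4.7.6 reports that "hearing loss occurred as early as the third cycle of CCNU, cisplatin, vincristine chemotherapy and as late as the seventh cycle". If this trial behaves similarly, grade 3–4 loss would be on record well before the audiogram that the rule reads, while recruitment to the arm continues.

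A Kaplan-Meier estimate is meant for staggered entry and incomplete follow-up. Fed by one reading at the end of treatment, it becomes little more than a late proportion among those who reached that reading. A patient with grade 3–4 loss during chemotherapy who dies before the final audiogram would add no event.

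A breach of 20% is not remote. Section 4.7.6 cites 32.3% grade 3–4 loss in that earlier study and 11% in the HIT 91 maintenance arm, one on each side of the limit.

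**Working it through.** **Timing of the earliest post-treatment audiogram (weeks after surgery)**

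- Surgery to start of RT: 28 to 40 days = 4.0 to 5.7 weeks (section 8.1).
- RT: standard arm 30 fractions ÷ 5 per week = 6.0 weeks; HFRT arm 68 ÷ 10 per week = 6.8 weeks (section 8.7.4).
- Gap before chemotherapy: 6 weeks. Chemotherapy: 8 courses × 6 weeks = 48 weeks (section 10.1).

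| | Standard arm | HFRT arm |
|---|---|---|
| Course 1 starts | 16.0–17.7 | 16.8–18.5 |
| Before course 4 (+18) | 34.0–35.7 | 34.8–36.5 |
| Before course 8 (+42) | 58.0–59.7 | 58.8–60.5 |
| End of course 8 (+48) | 64.0–65.7 | 64.8–66.5 |

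The last row is 14.7 to 15.3 months, with no delays allowed for. A final audiogram done straight after the last cisplatin dose would fall at about 13.3 to 13.9 months.

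**How much earlier pre-course audiology would show the loss**

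- Loss in cycle 3 is visible before course 4: 48 − 18 = 30 weeks earlier.
- Loss in cycle 7 is visible before course 8: 48 − 42 = 6 weeks earlier.

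**Further patients entering one arm in that time**

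The rates are those of section 13.10. The plan's own total reproduces from them: 2.8 × 33.6 + 2.2 × 102.7 = 94.1 + 225.9 = 320. Per arm, the count is (rate ÷ 2) × weeks ÷ 52.

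| Accrual per year | 6 weeks | 30 weeks |
|---|---|---|
| 33.6 (first 2.8 years) | 2 | 10 |
| 80 (stated for the last two years) | 5 | 23 |
| 102.7 (power calculation, n = 320) | 6 | 30 |

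**Share of the trial beyond the rule's reach**

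With a 15-month lag, patients readable when recruitment closes at 5 years are those entered by year 3.75: 94.1 + 0.95 × 102.7 = 192 of 320 (60%). With a 13.5-month lag, 204 of 320 (64%) are readable. The shorter lag also allows for the interval of up to 28 days between surgery and randomisation.

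**Patients who may never have the final audiogram**

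Under the constant hazards of section 13.10, the share with an EFS event by 15 months is 1 − S₃^(1.25/3):

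- standard arm: 1 − 0.70^0.417 = 13.8%
- HFRT arm: 1 − 0.85^0.417 = 6.5%

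This is an upper guide, because an event does not by itself prevent an audiogram. To illustrate the effect, assume that all these patients are missing, that their grade 3–4 rate is twice that of the others, and that 18% is observed. The true figure is then 0.862 × 18% + 0.138 × 36% = 20.5% in the standard arm and 0.935 × 18% + 0.065 × 36% = 19.2% in the HFRT arm. The bias is modest, but in the standard arm it is enough to cross the limit.

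**The case against.** The strongest reply is that section 13.7 speaks of a focus on post-treatment audiograms and does not exclude others. The sentence on events covers any grade 3 or 4 toxicity, and choosing a Kaplan-Meier estimate suggests that on-treatment events were meant to feed the curve, with the limit then read after treatment. This stands as a possible reading. It leaves a safety boundary with two meanings, and the wording needs the same repair under either.

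The trial also has other protection. Section 12 promises careful monitoring, and the DMSC sees toxicity every six months and may decide how the study proceeds. The chemotherapy toxicity form is returned after every second course (Appendix Q), and section 10.4.4 modifies platinum for the individual patient from the audiogram of the worse ear. All of this stands. None of it gives a trial-level figure for ototoxicity.

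The onset range belongs to an earlier study with different cisplatin modification criteria. Section 4.7.6 expects significantly less ototoxicity here and gives no onset timing under the HIT criteria. So 30 weeks and 23 patients describe the earliest-onset case, not a typical one.

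The pre-course requirement is for audiology, with pure tone audiometry only if possible. The pure tone audiogram at the end of treatment is mandatory without that qualifier, which is a fair reason to emphasise it. It is required of all patients entered, so stopping chemotherapy early does not exempt anyone; losses should be confined mainly to deaths and some relapses.

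Time origin and censoring are details that a statistical analysis plan may supply. Which audiograms the limit is read on, however, is fixed in section 13.7 itself.

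**Conclusion.** The point holds in limited form. Section 13.7 centres the only numeric ototoxicity limit on audiograms taken no earlier than about 15 months after surgery, although audiology on the same scale is required before every course. Read literally, the limit registers on-treatment grade 3–4 loss late, and not at all in patients who die or relapse before the final audiogram. For most patients who complete treatment the defect is one of timing.

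The gain from using the earlier results is about 6 to 30 weeks, or about 5 to 23 further patients per arm at 80 a year. This assumes the planned schedule and an onset range borrowed from an earlier study. It measures when a loss first becomes visible, not when an arm would cross 20%; that depends on the true rate and on the dates of the looks, which section 13.7 does not state.

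A reader might infer that excess ototoxicity would go unseen for 15 months, or that the rule ignores all on-treatment results. The documents do not support either: the wording leaves room for on-treatment events, the DMSC reviews toxicity every six months, and individual treatment is already modified by audiogram. A clarification of section 13.7 should be made, but nothing here shows that treated patients are left unmonitored.

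**What to change.** Keep the 20% limit and HIT grade 3–4. State in section 13.7 that the event is the first HIT grade 3–4 result on any scheduled audiogram (before each course, at the end of treatment, or later), timed from the start of RT, with each patient followed to the last audiogram.

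Put the per-arm Kaplan-Meier estimate and its confidence interval into the existing six-monthly DMSC report. Read it at the latest time with patients still at risk as well as at the end of treatment. Reading it only at the end of treatment would give back most of the earlier warning. Within one data cut the cumulative estimate cannot fall over time, so an arm already above 20% during chemotherapy will still be above it at the end-of-treatment reading.

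The cost is a change of wording and the use of audiology already required; no new tests are needed. There are two drawbacks. Early estimates will be imprecise, which is why the interval must be shown. Some pre-course tests in young children may not be pure tone audiograms, so the report should give the number of results obtained by each method.
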